2.4.1.2 Safety endpoints

Adverse events

AEs will be coded using the most recent version of the Medical Dictionary for Regulatory Activities.

A TEAE is defined as an event that has onset date on or after the first day of exposure to randomised treatment and no later than 7 days after the last day of randomised treatment. If the event has onset date before the first day of exposure on randomised treatment and increases in severity during the treatment period and until 7 days after the last drug date, then this event should also be considered as a TEAE. Here the first day of IMP administration is defined as the first day of exposure to randomised treatment.

TEAEs are summarised descriptively, whereas non-TEAEs are presented in listings. TEAE data will be displayed in terms of the number of subjects with at least one event (N), the percentage of subjects with at least one event (%), the number of events (E) and the event rate per 100 years of exposure (R).

Summaries of TEAEs and of serious TEAEs will be presented as an overview including all AEs, serious AEs, number of deaths, AEs by severity, AEs by relation to treatment and AEs of special interest including AEs leading to withdrawal.

Furthermore summary tables based on system organ class and preferred terms are made for:

- All TEAEs
- Serious TEAEs
- Possibly or probably related TEAEs
- Severe, moderate and mild TEAEs
- TEAEs reported by safety areas of interest
- TEAEs with preferred term that are experienced by at least 5% of the subjects in any treatment arm or by at least 5% of all subjects

A listing for non-TEAEs with onset date before the first day of exposure to randomised treatment will be presented. A listing will also be presented for non-TEAEs collected after the treatment emergent period according to the definition of TEAE.

Hypoglycaemic events

Data on treatment emergent hypoglycaemic episodes are presented in terms of the number of subjects with at least one event (N), the percentage of subjects with at least one event (%), the number of events (E) and the event rate per 100 years (R).

Separate summaries are made for severe or BG confirmed hypoglycaemic episodes, severe or BG confirmed symptomatic hypoglycaemic episodes, , nocturnal severe or BG confirmed symptomatic hypoglycaemic episodes and the ADA classification of hypoglycaemia.

The number of hypoglycaemic episodes during 26 weeks of treatment will be analysed separately for each endpoint using a negative binominal regression model with a log-link function and the logarithm of the time period in which a hypoglycaemic episode is considered treatment emergent as offset. The model will include treatment and pre-trial anti-diabetic treatment as fixed factor.

Clinical evaluations (physical examination, eye examination and ECG)

Eye examination (fundoscopy/fundus photography) and ECG findings will be summarised descriptively, including:

- summaries for each visit
- shift table from baseline to after 26 weeks of treatment

Any findings in the physical examination evaluation at screening will be presented as listings. Any clinically significant deterioration of a pre-existing condition after the screening visit, as well as any new clinically significant findings will be recorded as AEs.

Pulse

Change from baseline in pulse after 26 weeks of treatment will be analysed using the standard ANCOVA model.

Laboratory assessments

All laboratory parameters will be summarised descriptively.

The following tables will be presented based on both observed and LOCF imputed data:

- Shift tables from baseline to after 26 weeks of treatment
- Proportion of subjects with measurements outside reference range by treatment and week

Laboratory values will be presented graphically as box plots by treatment and week. For each laboratory parameter, individual values outside the reference ranges (abnormal values) will be listed.

Calcitonin

The purpose of the calcitonin analysis is to evaluate longitudinal changes in calcitonin, with main focus on subjects who develop persistently high levels of calcitonin during the trial.

Calcitonin will be displayed in terms of the number of subjects (N), the percentage of subjects (%) and the incidence rate per 100 years of exposure (R).

The following criteria are defined for tabulations:

Persistent (all post baseline measurements)

- From < UNR to persistently \geq UNR
- From < UNR to persistently \geq 1.5 UNR
- From < UNR to persistently \geq 20 ng/L
- From < UNR to persistently \geq 50 ng/L
- From < 20 ng/L to persistently \geq 20 ng/L
- From < 50 ng/L to persistently \geq 50 ng/L

Incidental (at least one post baseline measurements)

- From < UNR to \geq UNR
- From < UNR to \geq 1.5 UNR
- From < UNR to \geq 20 ng/L
- From < UNR to \geq 50 ng/L
- From < 20 ng/L to \geq 20 ng/L
- From < 50 ng/L to \geq 50 ng/L

The distribution of all calcitonin measurements across treatment groups and time will be shown with box plots and corresponding cumulative plots for actual levels of calcitonin and change from baseline. The plots will be presented by treatment group (using ET measurement - LOCF) and within treatment group by week. Plots will be done by each gender, separately.

Summaries tables of calcitonin continuous measurements, will include number and percentage of observations < and \geq lower limit of quantification (LLOQ), minimum, Q25, median, Q75 and maximum. Summaries will be presented for all subjects and by gender.

Longitudinal changes for subjects with calcitonin levels \geq 20 ng/L will be plotted (longitudinal plots). The plots will be done by treatment and gender. They will be done for subjects in the persistent and incidental categories, separately.

A listing of subjects with at least one post baseline value \geq 20 ng/L will be done. The listing will include age, gender, calcitonin measurements over time and AE history (including preferred term, onset and stop dates).

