1.1 Objectives and endpoints

Primary objective

To confirm the superiority of insulin degludec/liraglutide (IDegLira) vs. insulin degludec (IDeg) in controlling glycaemia in Japanese subjects with type 2 diabetes mellitus (T2DM) after 26 weeks of treatment.

Secondary objective

To compare the general efficacy and safety of IDegLira and IDeg after 26 weeks of treatment in Japanese subjects with T2DM.

Primary endpoint

Change from baseline in glycosylated haemoglobin (HbA_{1c}) after 26 weeks.

Key secondary endpoints

- Change from baseline in body weight after 26 weeks
- Change from baseline in fasting plasma glucose (FPG) after 26 weeks
- Number of treatment emergent severe or blood glucose (BG) confirmed hypoglycaemic episodes during 26 weeks of treatment

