- Change from baseline in patient reported outcomes (PROs) after 26 weeks of treatment:
 - Diabetes Therapy-Related QOL (DTR-QOL) questionnaire
 - EuroQol-5D (EQ-5D-5L) questionnaire

Key supportive secondary endpoints prospectively selected for disclosure (e.g. clinicaltrials.gov) are marked with an asterisk (*).

5 Trial design

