11.2 Stratification

To ensure an even proportion of subjects on pre-trial basal or pre-mix/combo insulin in each treatment arm, the randomisation will be stratified as in the following with regards to these two different pre-trial insulin therapies combined with metformin with or without one other OAD:

- metformin + basal insulin
- metformin + basal insulin + one other OAD
- metformin + pre-mix/combo insulin
- metformin + pre-mix/combo insulin + one other OAD

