17.4 Secondary endpoints

17.4.1 Supportive secondary endpoints

17.4.1.1 Efficacy endpoints

Insulin dose after 26 weeks of treatment

The actual daily dose after 26 weeks of treatment will be analysed using the standard ANCOVA model including treatment and pre-trial anti-diabetic treatment as fixed factors and baseline HbA_{1c} value and baseline insulin dose as covariates.

Responder after 26 weeks of treatment

Two dichotomous endpoints (responder/non-responder) will be defined based on whether a subject has met a specific target level after 26 weeks of treatment:

- HbA_{1c} < 7.0%
- HbA_{1c} ≤ 6.5%

Analysis of each of the two responder endpoints will be based on a logistic regression model with treatment and pre-trial anti-diabetic treatment as fixed factors and baseline HbA_{1c} values as a covariate.

HbA_{1c} responder endpoints without weight gain after 26 weeks of treatment

Responder for HbA_{1c} without weight gain after 26 weeks of treatment will be defined as HbA_{1c} < 7.0% or ≤ 6.5% at ET and change from baseline in body weight bellow or equal to zero. Analysis of each of the two responder endpoints will be based on a logistic regression model with treatment and pre-trial anti-diabetic treatment as fixed factors and baseline HbA_{1c} and baseline body weight values as covariates.

HbA_{1c} responder endpoints without hypoglycaemic episodes

Responder for HbA_{1c} without hypoglycaemic episodes after 26 weeks of treatment will be defined as HbA_{1c} < 7.0% or ≤ 6.5% at ET and without treatment emergent severe or BG confirmed symptomatic hypoglycaemic episodes during the last 12 weeks of treatment. Analysis of each of the two responder endpoints will be based on a logistic regression model with treatment and pre-trial anti-diabetic treatment as fixed factors and baseline HbA_{1c} values as a covariate.

HbA_{1c} responder endpoints without hypoglycaemic episodes and weight gain

Responder for HbA_{1c} without hypoglycaemic episodes and weight gain after 26 weeks of treatment will be defined as HbA_{1c} < 7.0% or ≤ 6.5% at ET, without treatment emergent severe or BG confirmed symptomatic hypoglycaemic episodes during the last 12 weeks of treatment, and change from baseline in body weight bellow or equal to zero. Analysis of each of the two responder endpoints will be based on a logistic regression model with treatment and pre-trial anti-diabetic treatment as fixed factors and baseline HbA_{1c} and body weight values as covariates.

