2.4 Secondary endpoints

2.4.1 Supportive secondary endpoints

2.4.1.1 Efficacy endpoints

Insulin dose after 26 weeks of treatment

The actual daily dose after 26 weeks of treatment will be analysed using the standard ANCOVA model including treatment and pre-trial anti-diabetic treatment as fixed factors and baseline HbA_{1c} value and baseline insulin dose as covariates.

Body weight

The change from baseline in body weight after 26 weeks of treatment will be analysed using the standard ANCOVA model with treatment and pre-trial anti-diabetic treatment as fixed factors and baseline body weight as covariate. Missing values after 26 weeks of treatment will be imputed applying LOCF using body weight values at and after baseline.

Responder after 26 weeks of treatment

Two dichotomous endpoints (responder/non-responder) will be defined based on whether a subject has met a specific target level after 26 weeks of treatment:

- HbA_{1c} < 7.0%
- HbA_{1c} ≤ 6.5%

Analysis of each of the two responder endpoints will be based on a logistic regression model with treatment and pre-trial anti-diabetic treatment as fixed factors and baseline HbA_{1c} values as a covariate.

HbA_{1c} responder endpoints without weight gain after 26 weeks of treatment

Responder for HbA_{1c} without weight gain after 26 weeks of treatment will be defined as HbA_{1c} < 7.0% or ≤ 6.5% at ET and change from baseline in body weight below or equal to zero. Analysis of each of the two responder endpoints will be based on a logistic regression model with treatment and pre-trial anti-diabetic treatment as fixed factors and baseline HbA_{1c} and baseline body weight values as covariates.

HbA_{1c} responder endpoints without hypoglycaemic episodes

Responder for HbA_{1c} without hypoglycaemic episodes after 26 weeks of treatment will be defined as HbA_{1c} < 7.0% or ≤ 6.5% at ET and without treatment emergent severe or BG confirmed symptomatic hypoglycaemic episodes during the last 12 weeks of treatment. Analysis of each of the two responder endpoints will be based on a logistic regression model with treatment and pre-trial anti-diabetic treatment as fixed factors and baseline HbA_{1c} values as a covariate.

HbA_{1c} responder endpoints without hypoglycaemic episodes and weight gain

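### The hypoglycaemia count models use no continuous baseline covariate; adding baseline HbA1c and pre-trial insulin dose is a cheap, low-severity gain in precision

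*SAP*

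**What the plan says.** SAP 2.4.1.2 and Protocol 17.4.1.2 specify the same analysis for every hypoglycaemia endpoint: a "negative binominal regression model with a log-link function", with "the logarithm of the time period in which a hypoglycaemic episode is considered treatment emergent as offset". On the terms, the SAP says "The model will include treatment and pre-trial anti-diabetic treatment as fixed factor". The pre-trial treatment factor has four levels and is the one used at randomisation, where Protocol 11.2 says "the randomisation will be stratified as in the following". Neither document names a variance estimator for these models or plans a sensitivity analysis specific to them.

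Most other models in the plan carry a continuous baseline value. The standard ANCOVA includes the baseline of the variable analysed, also for pulse, which is a safety endpoint. The HbA1c responder models in Protocol 17.4.1.1 use "treatment and pre-trial anti-diabetic treatment as fixed factors and baseline" HbA1c. The insulin dose analysis in SAP 2.4.1.1 takes baseline HbA1c "value and baseline insulin dose as covariates".

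Protocol 1.1 lists "Number of treatment emergent severe or blood glucose (BG) confirmed hypoglycaemic episodes during 26 weeks of treatment" among the key secondary endpoints. Protocol 4.2.2.1 explains the label: "Key supportive secondary endpoints prospectively selected for disclosure".

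**The concern.** Subjects enter with HbA1c anywhere from 7.5% to 11.0% and 20 to 50 units of insulin a day (Protocol 6.1), and all are titrated to one fasting target. Distance from that target and previous insulin requirement could plausibly explain part of the differences in episode rate between subjects. Where a covariate does so, leaving it out makes the estimated rate ratio more variable than it needs to be.

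A baseline hypoglycaemia count would be the obvious covariate, but episodes are recorded only from randomisation (Protocol 8.5.7). HbA1c and insulin dose are therefore the natural candidates. What is at stake is the width of the interval around a rate ratio that will be disclosed, and that bears on the reduced hypoglycaemia argued for in Protocol 3.2.

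**Working it through.** **Is there a figure to reproduce?** Not for hypoglycaemia. The documents give no episode rate, dispersion, rate ratio or power for it. The only design calculation is for HbA1c: 0.85 × 0.45 + 0.15 × 0.20 = 0.4125, which with SD 1.0 and 105 per arm gives 84.5% power in a two-sample t-test, as stated in Protocol 17.1. It says nothing about this endpoint.

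**From the documents:** 105 per arm, 1:1; 15% withdrawal; a four-level factor; a log-time offset; two-sided 95% intervals.

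**Assumed, because the documents are silent:** episode rate, rate ratio, form and size of between-subject heterogeneity, and prognostic strength of the covariates.

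**Model.** log E(Y) = log(time) + a + b·treatment + stratum, with or without a term for baseline. Under randomisation and a log link, adding the baseline term does not change what exp(b) means.

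**Precision, by share of log-rate variance explained** (simulation; mean 1.25 episodes per IDeg subject, rate ratio 0.6). The last column is 1/(1 − fall)² − 1, for example 1/0.95² − 1 = 0.108.

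| Share explained | Fall in empirical SD of log rate ratio | Fall in reported SE | Equivalent extra subjects |
|---|---|---|---|
| 5% | about 2-3% | about 1% | 4-6% |
| 10% | about 5% | about 2% | 11% |
| 20% | about 8-12% | about 5% | 18-29% |
| not prognostic | near zero | near zero | none |

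A further run of 1,500 replicates with log-normal heterogeneity (log-variance 2) gave SD ratios of 0.986, 0.958 and 0.919, that is falls of 1.4%, 4.2% and 8.1%. This is the same picture, slightly lower.

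**Precision, by covariate slope** (a different scale: 3 episodes per patient-year, dispersion 2, rate ratio 0.6, 1,000 replicates, one standardised covariate).

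| Log-rate slope per SD | Empirical SD without / with | Variance ratio | Mean model SE without / with | Coverage of model-based 95% interval without / with |
|---|---|---|---|---|
| 0.2 | 0.248 / 0.242 | 0.96 | 0.240 / 0.238 | 94.3% / 95.1% |
| 0.4 | 0.264 / 0.245 | 0.86 | 0.248 / 0.241 | 94.2% / 94.7% |
| 0.6 | 0.281 / 0.244 | 0.75 | 0.259 / 0.245 | 92.8% / 95.5% |
| 0.8 | 0.326 / 0.264 | 0.66 | 0.278 / 0.254 | 90.6% / 93.9% |

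The printed interval changes little at moderate strength. At slope 0.4 and a rate ratio of 0.6, exp(1.96 × 0.248) = 1.626 gives 0.37 to 0.98, and exp(1.96 × 0.241) = 1.604 gives 0.37 to 0.96. The empirical SD falls more than the reported SE because the unadjusted model-based SE is somewhat too small when a strong covariate is omitted.

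**Variance estimator, a secondary matter** (105 per arm, nominal 95%; assumed rates of 1.5 to 4 per patient-year except in the second row).

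| Heterogeneity | Model-based coverage | Sandwich coverage |
|---|---|---|
| Gamma (model correct) | 93-95% | 92-94% |
| Log-normal, log-variance 3 (mean 1.25 per IDeg subject) | about 84% | about 88% |
| Log-normal, log-variance ln(1+3) = 1.39 | 88-92% | 92-95% |
| Dispersion 2 in one arm, 6 in the other | 90-92% | about 92% |
| Zero-inflated | 94-97% | 93-94% |

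With 1,000 replicates the simulation error of a coverage near 95% is √(0.95 × 0.05/1000) = 0.7 points.

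**The case against.** The plan's model is complete and respects the stratification. The standard ANCOVA adjusts for the baseline of the variable analysed, and a hypoglycaemia count has none. Nor do the composite responders show that the sponsor regards HbA1c as a predictor of hypoglycaemia. The HbA1c-without-hypoglycaemia responder has the same covariates as the plain HbA1c responder, while the weight composites add baseline weight. HbA1c is there because it is part of the endpoint. Pre-trial insulin is also stopped and both arms restart at 10 to 16 units or dose steps, which may weaken the link between previous dose and later episodes.

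All of this stands. It shows that the omission is not an error, and that the prognostic strength is unknown and possibly small. It does not remove the case for using two values that are already recorded, when the cost is near zero even if they turn out to be uninformative.

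A reader might also infer that the planned interval rests on the model-based variance and is too narrow. The documents name no estimator. Even if the usual model-based one is used, its coverage is near nominal under gamma heterogeneity and can be conservative under zero inflation. The sandwich recovers only about 2 to 4 points under heavy tails and is no better when the model is right, so the case for making it primary is not made. SAP section 2 also allows outliers to be examined in sensitivity analyses, though only if deemed relevant.

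**Conclusion.** The point holds as a low-severity, nearly free improvement. The models adjust for one baseline characteristic, the four-level factor, and for no continuous one. Under the assumed inputs, adding baseline HbA1c and pre-trial insulin dose lowers the empirical SD of the log rate ratio by about 2-3%, 5% or 8-12% if they explain 5%, 10% or 20% of the between-subject log-rate variance. Every one of these figures depends on assumptions that the documents cannot confirm.

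Two stronger readings are not supported. That precision is certainly being lost would need evidence that the covariates are prognostic, and the documents give none. That a confirmatory result is weakened misreads the label: here key means selected for disclosure, the endpoint is supportive, and only HbA1c carries the superiority claim.

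**What to change.** In SAP 2.4.1.2, add baseline HbA1c and pre-trial total daily insulin dose as continuous covariates to each negative binomial model. State in advance that, if a sparse endpoint such as nocturnal episodes does not converge, the analysis reverts to treatment and pre-trial anti-diabetic treatment alone. Name the variance estimator. Optionally, report a robust-variance interval as a sensitivity analysis and not as the primary inference: if the primary interval is model-based, its coverage under heavy-tailed heterogeneity may be about 84-90%, against about 88-93% with the sandwich.

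The cost is a few sentences and two model terms, settled before data are released for analysis. No new data are needed. Both values are checked at screening as eligibility criteria (Protocol 6.1), the pre-trial insulin dose is recorded under Protocol 8.3.4, and the SAP already uses the screening value when the randomisation value is missing. Few subjects, if any, should be lost from the models.

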2.4.2 Patient reported outcomes

The following questionnaires will be used to compare PROs between treatments:

- DTR-QOL questionnaire
- EQ-5D-5L questionnaire

The questionnaires will be summarised descriptively by visit and treatment.

For the DTR-QOL questionnaire change from baseline in the following scores will be analysed separately using the standard ANCOVA:

- Domain QOL scores
 - Burden on social activities and daily activities
 - Anxiety and dissatisfaction with treatment
 - Hypoglycemia
 - Satisfaction with treatment
- Total QOL score

For the EQ-5D-5L questionnaire change from baseline in QOL and VAS scores will analysed separately using the standard ANCOVA.

Quality Adjusted Life Years will be evaluated in a separate report by the Novo Nordisk Health Economics and Outcomes Research department.

3 Changes to the statistical analyses planned in the protocol

Corrections have been made to the supportive secondary endpoints. The description of analysis of change from baseline in body weight after 26 weeks of treatment has accidentally been left out of protocol, however listed in the endpoint section of the protocol.

Additional sensitivity analysis for change from baseline in HbA_{1c} has been added to further evaluate the impact of protocol amendment 2 (08-Sep-2016) implemented during recruitment of subjects for this trial. In this amendment inclusion and exclusion criteria was changed, therefore a sensitivity analysis comparing treatment difference in subjects recruited by one set of criteria will be compared to ones recruited with updated set of criteria.

Box plots have replaced the planned histograms for calcitonin.

4 References

1. International Conference on Harmonisation. ICH Harmonised Tripartite Guideline. Statistical principles for clinical trials E9. International Conference on Harmonisation E9 Expert Working Group. September 1998.

Statistical Analysis Plan
Trial ID: NN9068-4184
UTN: U1111-1178-3453
EudraCT No.: NA

~~CONFIDENTIAL~~

Date:	08 December 2017	Novo Nordisk
Version:	1.0	
Status:	Final	
Page:	14 of 14	

